2.2 Study Objectives

The purposes of this clinical trial are to evaluate the efficacy and safety of FS Grifols as an adjunct to achieve hemostasis during surgery in pediatric subjects.

2.2.1 Efficacy Objectives

2.2.1.1 Primary Efficacy Objective

• To evaluate if FS Grifols is non-inferior to EVICEL in terms of the proportion of subjects achieving hemostasis at the TBS by 4 minutes (T₄) from the start of treatment application (T_{Start}) with no occurrence of rebleeding until the completion of the surgical closure by layers of the exposed surgical field containing the TBS (T_{Closure})

2.2.1.2 Secondary Efficacy Objectives

- To determine the cumulative proportion of subjects achieving hemostasis at the TBS by the defined observation time points of T_7 and T_{10}
- To determine prevalence of treatment failures

2.2.1.3 Exploratory Efficacy Objectives

- To determine the proportion of subjects achieving at least 1 point decrease in bleeding intensity according to the 5-point validated bleeding severity scale at the defined observation time points of T₄, T₇, and T₁₀
- To determine the mean change from baseline in bleeding intensity according to the 5-point validated bleeding severity scale at the defined observation time points of T₄, T₇, and T₁₀

Page 7 of 18

2.2.2 Safety Objective

• To evaluate the safety and tolerability of FS Grifols in pediatric subjects undergoing surgery

3 STUDY VARIABLES

3.1 Efficacy Measures

For surgical procedures in both treatment groups, the following data will be collected and recorded to assess the efficacy of hemostasis by the investigator (surgeon):

T _{Start}	time of start of initial study treatment application to TBS
T_{End}	time of end/completion of initial study treatment application to TBS
T _{Start2}	time of start of study treatment reapplication after T_{End} and before T_{4} , if applicable
T _{End2}	time of end/completion of study treatment reapplication, if applicable
T ₄	hemostatic assessment at 4 minutes following T _{Start}
T ₇	hemostatic assessment at 7 minutes following T _{Start}
T ₁₀	hemostatic assessment at 10 minutes following T _{Start}
Tclosure	time of completion of the surgical closure by layers of the exposed surgical field containing the TBS
T _{Completion}	time of completion of the surgical incision closure – when the last skin closure stitch is put in – of the last exposed field, regardless of whether it was the field containing the TBS

Unless otherwise noted, if an observation is missing at a specific scheduled visit/time point, the value at that visit should not be imputed and should be reported as "missing". Hemostasis assessment is an exception. A missing hemostasis assessment at any scheduled time point will be deemed not to have achieved hemostasis at that specific time point only.

The 5-point validated bleeding severity scale is used to assess the hemostasis and shown below:

Table 3-1 Validated Bleeding Severity Scale

Grade	Visual Presentation	Anatomic Appearance	Qualitative Description	Visually Estimated rate of Blood Loss (mL/min)
0	No bleeding	No bleeding	No bleeding	≤1.0
1	Ooze or intermittent flow	Capillary-like bleeding	Mild	>1.0-5.0
Grifols Worldwide	e Operations, Ltd	Page 7 of 18		Version 1.0

Page 8 of 18

Table 3-1 Validated Bleeding Severity Scale

Grade	Visual Presentation	Anatomic Appearance	Qualitative Description	Visually Estimated rate of Blood Loss (mL/min)
2	Continuous flow	Venule and arteriolar-like	Moderate	>5.0-10.0
		bleeding		
3	Controllable spurting	Noncentral venous- and	Severe	>10.0-50.0
	and/or overwhelming	arterial-like bleeding		
	flow			
4	Unidentified or	Central arterial- or	Life threatening ^a	>50.0
	inaccessible spurting	venous-like bleeding		
	or gush			

^a Systemic resuscitation is required (eg, volume expanders, vasopressors, blood products, etc).

3.1.1 Primary Efficacy Variable

The primary efficacy variable is the proportion of subjects achieving hemostasis (binary decision: hemostatic response, Grade $0 = \text{Yes/Grade} \ge 1 = \text{No}$) at the TBS by T_4 without occurrence of rebleeding or reapplication of study treatment after T_4 and until T_{Closure} , and without Grade 3 or Grade 4 bleeding, or use of alternative hemostatic treatment after T_{Start} and until T_{Closure} . Hemostasis is defined as Grade 0 bleeding at the TBS according to the investigator's (surgeon's) judgment, so that the surgical closure of the exposed field could begin. Rebleeding is defined as Grade ≥ 1 bleeding from the TBS requiring further hemostatic intervention (eg, manual pressure) after hemostasis was previously achieved at the TBS.

The primary efficacy endpoint of hemostasis by T₄ is shown below.

	H	emostas	is	Was study	Did the TBS re-bleed	Primary
	ac	chieved'	?a	treatment re-	after the 10 minute	Efficacy
				applied at	observation period and	Endpoint:
				TBS after T ₄	before T _{Closure} , or was	Hemostasis
				and before	alternative hemostatic	by T ₄ ?
				T _{Closure} ? ^b	treatment used at the	
					TBS, or was there Grade	
					3 or Grade 4 bleeding at	
					TBS during the 10-	
					minute observational	
					period and until T _{Closure} ? ^b	
					period and antir Telosure:	
Scenario	T ₄	T ₇	T ₁₀			
Section	14	1 /	110			

1	Yes	Yes	Yes	No	No	Yes
2	No	No a	Yes or at any point	Either Yes or No	Either Yes or No	No
3	Either Yes or No		nt any point	Either Yes or No	Either Yes or No	No
4	Eithe	er Yes o	r No	Yes	Either Yes or No	No
5	Eithe	Either Yes or No		Either Yes or No	Yes	No

Page 9 of 18

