#### 6.3 **Prohibited Concomitant Medications during the Study**

Use of an alternative hemostatic product or treatment (including application of manual pressure) during the 10-minute observational period, apart from reapplication of FS Grifols or EVICEL before T4, is prohibited, unless there is Grade 3 or 4 (see Table 7-1) breakthrough bleeding at the TBS that jeopardizes subject safety according to surgeon's judgment, in which case the surgeon may use any other hemostatic measure at his/her discretion (the use of FS Grifols, EVICEL, or other plasma-derived hemostatic agents are not allowed in this case). FS Grifols or EVICEL cannot be used as hemostatic treatment for any non-TBS.

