### 7.2.1.3.3 OBSERVATIONAL PERIOD

An observational period of 10 minutes will occur following TStart to determine whether hemostasis has been achieved at the TBS as described in Section 7.2.1.3.2.

- Vital signs (HR, RR [indicate if the subject is or is not under mechanical ventilation when the measure is taken], SBP and DBP, and T) will be recorded at 5 minutes after TStart.
- Confirmation of existing and recording of any new medications, except gaseous
  anesthetics, or changes in medications administered to the subject since the last
  assessment (it includes also any blood products administered to the subject). Use of
  anticoagulants and any neutralizing agent should be also recorded in detail including dose
  and time of administration.

• Assessment of hemostasis.

Hemostasis at the TBS will be assessed by the investigator (surgeon) at T4, T7, and T10. Hemostasis is defined as an absence/cessation of bleeding (Grade 0) at the TBS according to the investigator's (the surgeon's) judgment, so that the surgical closure of the exposed field could begin.

In order to facilitate the observation of hemostasis, investigators should remove any excess of accumulated blood around the TBS area by careful aspiration/suction and/or gentle sponging with the edge of a sterile pad, for instance.

Rebleeding is defined as Grade ≥1 bleeding from the TBS that requires further hemostatic intervention (e.g., manual pressure) after hemostasis is previously achieved at the TBS. If the TBS rebleeds but cessation of rebleeding is again achieved at a later time point, the effective hemostatic time point will be when the cessation of rebleeding happened.

Assessment of AEs.

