3.1.2.2 Prevalence of Treatment Failures

The following cases will be considered treatment failures:

- Persistent bleeding at the TBS beyond T₄
- Grade 3 or Grade 4 breakthrough bleeding from the TBS that jeopardizes subject safety according to the investigator's judgment at any moment during the 10-minute observational period and until T_{Closure}
- Use of alternative hemostatic treatments or maneuvers (other than the study treatment) at the TBS during the 10-minute observational period and until $T_{Closure}$, or use of study treatment at the TBS beyond T_4 and until $T_{Closure}$
- Rebleeding (Grade ≥1) at the TBS after the assessment of the primary efficacy endpoint at T₄ and until T_{Closure}

In the event of Grade 3 or Grade 4 breakthrough bleeding that jeopardizes subject safety according to the investigator's judgment at the TBS at any moment during the 10-minute observational period and until the completion of the surgical closure by layers of the exposed

^a Any missing to the question will be deemed "No".

^b Any missing to the question will be deemed "Yes".

Grifols Worldwide Operations, Ltd

Page 10 of 18

surgical field, the surgeon may use any other hemostatic measures at his/her discretion if
deemed necessary (use of FS Grifols, EVICEL, or other plasma-derived hemostatic agents
are not allowed in this case). In such a case, the subject will be considered a treatment failure.

The alternative treatment used will be recorded in the subject's source documents and
electronic case report forms (eCRFs).

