4 GENERAL STATISTICAL CONSIDERATIONS

Statistical analyses and data presentations will be generated using SAS version 9.4 or higher.

Unless otherwise noted, for continuous variables, descriptive statistics will include the number of non-missing values, mean, standard deviation, median, minimum and maximum. For categorical variables, descriptive statistics will include counts and percentages per category. All statistical inference will be tested at 2-sided with α =0.05.

Unless otherwise noted, all data collected in the eCRFs or electronically transferred (such as central laboratory data) will be presented in data listings. Subjects will be identified in the data listings by subject number (which includes site number) and grouped by different treatment groups.

For table summaries, the data will be presented at the scheduled visits according to protocol. Any data collected at the unscheduled visits will be listed.

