4.3 Sample Size Considerations

The sample size of the study was estimated to provide sufficient power (at least 80%) to demonstrate the hemostatic efficacy of FS Grifols in parenchymous and soft tissue surgery.

Assuming that the true response rate is 80% for the FS Grifols group and 80% for the EVICEL group, it can be shown that a sample size of 172 subjects (86 subjects in the FS Grifols treatment group and 86 subjects in the EVICEL treatment group, with a 1:1 assignment ratio) would give a power of at least 80% to establish non-inferiority, with lower 95% CI for the ratio of the proportion of subjects with hemostasis success by 4 minutes in the 2 treatment groups (FS Grifols relative to EVICEL) above 0.80.

The approximate number of subjects planned to be randomized according to age range will be as follows:

Grifols Worldwide Operations, Ltd Page 12 of 18

- Adolescents (12 to 17 years): approximately 100
- Children (2 to 11 years): approximately 50
- Infants and toddlers (28 days to 23 months): approximately 16
- Preterm (up to gestational age <37 weeks) and term newborn infants (0 to 27 days): approximately 6

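### The SAP 3.1.1 scoring table starts its rebleeding question after the 10-minute period, not at T4, leaving a narrow gap for untreated Grade 1–2 rebleeds that stop before the next reading

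*SAP*

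**What the plan says.** **Text of the endpoint.** SAP 3.1.1 and Protocol 7.1.1 require Grade 0 at the target bleeding site by T4 without "occurrence of rebleeding or reapplication of study treatment after" T4 and until TClosure. They also require no Grade 3 or 4 bleeding and no alternative hemostatic treatment from TStart until TClosure. SAP 3.1.1 defines rebleeding as Grade 1 or higher bleeding that requires further hemostatic intervention, with manual pressure as its example, after hemostasis had been reached.

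**Scoring table.** The table in SAP 3.1.1 has columns for the T4, T7 and T10 readings, for reapplication between T4 and TClosure, and for a combined question. The rebleeding part of that question covers only the time "after the 10 minute" observation period and before TClosure. The alternative-treatment and Grade 3/4 parts cover the 10 minutes as well. Scenario 1 (Yes at all three readings, No to both questions) is success.

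**Treatment failures.** SAP 3.1.2.2 lists rebleeding of Grade 1 or higher "at the TBS after the assessment of the primary efficacy endpoint at" T4 and until TClosure. It does not repeat the intervention element.

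**Conduct between T4 and T10.** Protocol 6.1 allows no study product after T4. Under Protocol 6.3, "Use of an alternative hemostatic product or treatment (including application of manual pressure) during the 10-minute observational period" is prohibited apart from reapplication before T4, unless there is Grade 3 or 4 breakthrough bleeding that endangers the subject.

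**Re-timing.** Protocol 7.2.1.3.3 says: "If the TBS rebleeds but cessation of rebleeding is again achieved at a later time point", hemostasis is dated from when the rebleeding ceased. The SAP does not repeat this rule.

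**The concern.** The sentence and the table in SAP 3.1.1 start the rebleeding clock at different times, T4 and T10. Between those times the table relies on two point readings and on flags for treatment given or for severe bleeding. A bleed that starts after T4 and stops before the next reading is visible to neither if it is Grade 1–2 and untreated. For such bleeds the protocol bars both study product and other measures, so in a compliant case the flags stay at No.

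At stake is whether the programmed endpoint measures what the stated endpoint describes. A child could be recorded as a treatment failure for rebleeding and also count as a primary success. If such events differed by product, the ratio would move, in either direction. If the mismatch is found only after unblinding, someone must then choose between text and table with the results known.

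**Working it through.** **1. The plan's own figure.** The SAP uses a two-sided test ("All statistical inference will be tested at 2-sided with" α = 0.05), a margin of 0.8 on the ratio, 86 subjects per arm, and this assumption: "Assuming that the true response rate is 80% for the FS Grifols group and 80% for the" EVICEL group. It says that this "would give a power of at least 80% to establish non-inferiority". On the log-ratio scale:

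- SE = √(2 × (0.2/0.8)/86) = √(0.5/86) = 0.0762
- −ln(0.8)/SE = 0.2231/0.0762 = 2.93
- power = Φ(2.93 − 1.96) = 83.3%

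Exact enumeration of the interval gives 82.7%, and simulation of the stratified SAP 9.1 formula (43 per arm per stratum) gives 82.8%. The stated power is reproduced and is not in question.

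**2. What the table does with a Grade 1–2 bleed between T4 and T10.** Each row starts from Grade 0 at T4.

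| At the next reading | Intervention given | Table result | Reason |
|---|---|---|---|
| Still bleeding | None | Failure | T7 or T10 = No |
| Still bleeding | Study product | Failure | Reading and reapplication |
| Still bleeding | Manual pressure or other | Failure | Reading and alternative treatment |
| Stopped | Study product | Failure | Reapplication (scenario 4) |
| Stopped | Manual pressure or other | Failure | Alternative treatment (scenario 5) |
| Stopped | None | **Success** | No column records it (scenario 1) |

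Grade 3 or 4 bleeding is failure on every path. One path in six departs from failure.

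**3. What the text says about the sixth path.** There are two cases.

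- The surgeon did not think intervention was needed. The bleed is then not rebleeding under the SAP 3.1.1 definition, and success is consistent with the text. It still meets the treatment-failure list if that list's Grade 1 or higher wording is read alone.
- The surgeon judged intervention to be required but withheld it, as the protocol directs. The bleed then meets the definition, and the text gives failure. The re-timing rule agrees: hemostasis is dated after T4, so it was not achieved by T4. The table gives success.

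**4. Size.** The documents give no rate for the second case, so the rates below are assumed. With one stratum, the SAP 9.1 standard error reduces to √(1/a − 1/86 + 1/b − 1/86), where a and b are the successes in the FS Grifols and EVICEL arms. I enumerated both binomials and summed the probability that the lower limit exceeds 0.8. The text-defined rates are set at 64% and 80%, a true ratio of 0.80; the table-scored rates add the missed points.

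| Points missed, FS Grifols / EVICEL | Table-scored rates | Chance of declaring non-inferiority |
|---|---|---|
| 0 / 0 | 64% / 80% | 2.9% |
| 2 / 2 | 66% / 82% | 3.4% |
| 1 / 0 | 65% / 80% | 4.1% |
| 2 / 0 | 66% / 80% | 5.7% |
| 0 / 2 | 64% / 82% | 1.6% |
| 4 / 2 (illustrative) | 68% / 82% | 6.8% |
| 4 / 0 (illustrative) | 68% / 80% | 10.6% |
| 8 / 4 (illustrative) | 72% / 84% | 14.7% |

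One point is 0.86 of a child per arm; 4 and 8 points are about 3 and 7 children of 86.

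**The case against.** The strongest reply is that rebleeding is, by definition, bleeding that requires intervention. If intervention was given, the table already scores failure. If none was given and the bleed stopped within about three minutes, that is itself evidence that none was required. Read with the same definition, the treatment-failure list does not contradict the table either. Further, the SAP nowhere says that the table overrides the sentence above it, and the re-timing rule, if applied to the T4 entry, would already produce a failure.

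Much of this stands. A reader might infer that any rebleed between T4 and T10 that has stopped by the next reading is counted as success against the written definition. The documents do not support that: treated bleeds score as failures, and a bleed that never required treatment is not clearly a failure under the text. A reader might also take 10.6% or 14.7% as the false-positive risk. Nothing in the documents supports misses of 4 to 8 points, or an imbalance between arms.

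Three things remain. Requiring intervention is not the same as receiving it, and in this window the protocol separates the two for Grade 1–2 bleeding. The re-timing rule is absent from the SAP, whose primary analysis (SAP 9.1) works from the nominal T4 reading. And a programmer will code from the table.

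One caution: the cells of scenarios 2 and 3 are broken in the text available to me. If their reference to any point in time was meant to cover the whole interval rather than the T7 and T10 readings, the gap would be closed. The point rests on the column heading and scenario 1, which are legible.

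**Conclusion.** The mismatch in start time is real and lies within one SAP section. Its consequence is limited to one path: a Grade 1–2 rebleed between T4 and T10, judged to require intervention, left untreated under the protocol, and stopped by the next reading. There the table gives success, while the written definition and Protocol 7.2.1.3.3 point to failure. The treatment-failure list points the same way only if its grade wording is read alone.

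The effect is probably small. For small assumed misses, the chance of declaring non-inferiority at a true ratio of 0.80 goes from 2.9% to 3.4% (2 points in each arm) or 4.1% (1 point, FS Grifols only). A miss confined to EVICEL works the other way (1.6% at 2 points). These figures assume 86 per arm, a single stratum and the stated rates; the frequency of such events is unknown. The sample size and stated power are unaffected as written. Severity: minor.

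**What to change.** In the SAP 3.1.1 table, start the rebleeding question at T4, for example: *Did the TBS re-bleed (as defined above) after T4 and before TClosure, …*, leaving the rest of the column as it is. Derive the answer from the rebleeding and treatment-failure records. The protocol synopsis already has treatment failures recorded during the observational period; the sponsor should confirm that the record identifies rebleeding and its time.

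Also state, before unblinding, how a transient Grade 1–2 bleed that stops untreated is scored, and apply the same rule to the primary endpoint and to SAP 3.1.2.2. That statement should say whether the intervention element applies to the treatment-failure list, and whether the re-timing rule in Protocol 7.2.1.3.3 governs the T4 result. This concerns scoring only and changes nothing in how bleeding is managed.

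The cost is one column heading, one sentence and the matching derivation. The success rate may fall slightly. If the 80% planning rate describes the table-scored endpoint and the fix removed 1 or 2 points from both arms, log-ratio power at 86 per arm would go from 83.3% to 81.0% or 78.7%. If the 80% already describes the endpoint as worded, power does not change.

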3.1.2 Secondary Efficacy Variables

3.1.2.1 Cumulative Proportion of Subjects Achieving Hemostasis at the Target Bleeding Site by the Time Points of T_7 and T_{10}

The cumulative proportion of subjects achieving hemostasis at the TBS by the time points of T_7 and T_{10} defined as an absence/cessation of bleeding (Grade 0) at the TBS by that time point without occurrence of rebleeding, Grade 3 or Grade 4 bleeding, use of alternative hemostatic treatment, and reapplication of study treatment after T_4 and until $T_{Closure}$.

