#### 7.1.1 Primary Efficacy Variable

The primary efficacy variable is the proportion of subjects achieving hemostasis (binary decision: hemostatic response, Grade  $0 = \text{Yes/Grade} \ge 1 = \text{No}$ ) at the TBS by T4 without occurrence of rebleeding or reapplication of study treatment after T4 and until TClosure, and without Grade 3 or 4 bleeding or use of alternative hemostatic treatment after TStart and until TClosure. Hemostasis is defined as Grade 0 bleeding at the TBS according to the investigator's (surgeon's) judgment, so that the surgical closure of the exposed field could begin.

Rebleeding is defined as Grade >1 bleeding from the TBS requiring further hemostatic intervention (e.g., manual pressure) after hemostasis was previously achieved at the TBS.

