#### 7.1.2 Secondary Efficacy Variable(s)

#### Cumulative Proportion of Subjects Achieving Hemostasis at the Target Bleeding 7.1.2.1 Site by the Time Points of T7 and T10

The cumulative proportion of subjects achieving hemostasis at the TBS by the time points of  $T_7$  and  $T_{10}$  defined as an absence/cessation of bleeding (Grade 0) at the TBS by that time point without occurrence of rebleeding, Grade 3 or 4 bleeding, use of alternative hemostatic treatment, and reapplication of study treatment after T4 and until TClosure.

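### The T7/T10 success definition gives rescue and Grade 3/4 bleeding one shared post-T4 window, so it can be read to score a child rescued before T4 as a later success

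*SAP*

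**What the plan says.** **T7/T10 success.** SAP 3.1.2.1 requires Grade 0 at the target bleeding site by the assessment in question, under this condition: "without occurrence of rebleeding, Grade 3 or Grade 4 bleeding, use of alternative hemostatic treatment, and reapplication of study treatment after". The window that closes this list runs from T4 to TClosure. Protocol 7.1.2.1 has the same structure: "without occurrence of rebleeding, Grade 3 or 4 bleeding, use of alternative hemostatic treatment, and reapplication of study treatment after". Its list closes with the same T4-to-TClosure window. The protocol synopsis repeats it under the secondary efficacy variables. Four events share one list with one closing window.

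**Primary variable.** SAP 3.1.1 uses two clauses with two start times. The first excludes "occurrence of rebleeding or reapplication of study treatment after T_4" and until TClosure. The second requires a course "without Grade 3 or Grade 4 bleeding, or use of alternative hemostatic treatment after" TStart and until TClosure. Protocol 7.1.1 agrees: "without Grade 3 or 4 bleeding or use of alternative hemostatic treatment after" TStart.

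**Treatment failure.** SAP 3.1.2.2 counts "Use of alternative hemostatic treatments or maneuvers (other than the study treatment) at the TBS during the 10-minute observational period" and on to TClosure, so the minutes before T4 are included.

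**Rescue and reapplication.** Protocol 6.1 permits other hemostatic measures within the 10-minute observation period when Grade 3/4 breakthrough bleeding endangers the child. It also permits reapplication of study product before T4.

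**Analysis.** SAP 9.2 says the T7 and T10 proportions are analysed by a CMH test in the same way as the primary. It gives no rule for deriving success. The scenario table in SAP 3.1.1 covers the T4 endpoint only.

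**The concern.** The T7 and T10 rates should be later-time versions of the primary endpoint, adding children whose bleeding stopped on study product after T4. The start time for rescue and severe bleeding, which the primary states explicitly, is absent from the later endpoints. If the single closing window covers the whole list, these events do not disqualify a child when they occur between TStart and T4. Hemostasis produced by another agent could then be credited to FS Grifols or EVICEL.

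Treatment-failure status does not close the gap. Bleeding beyond T4 is itself a treatment failure, and children who stop bleeding between T4 and T10 are exactly those the later endpoints are meant to add. A treatment failure can therefore properly be a T7 success, so a programmer cannot use the failure flag to exclude rescued children.

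At stake are the reported T7 and T10 rates and ratios, and whether two programmers would score the same child alike.

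**Working it through.** **1. The plan's own figure.** The plan gives no rate or power for T7/T10. The nearest figure is the primary's power of at least 80% (SAP 4.3), with p = 0.80 in both arms, n = 86 per arm and ratio margin 0.80.

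- SE(ln RR) = √[2(1 − p)/(pn)] = √(0.4/68.8) = 0.07625
- Power = Φ(0.2231/0.07625 − 1.96) = Φ(0.966) = 83.3%

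The stated power reproduces, and this point does not touch it.

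**2. Event windows side by side** (each runs to TClosure)

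| Event | Primary | T7/T10, window on whole list | T7/T10, window on reapplication only |
|---|---|---|---|
| Rebleeding | after T4 | after T4 | none stated |
| Reapplication | after T4 | after T4 | after T4 |
| Grade 3/4 bleeding | after TStart | after T4 | none stated |
| Alternative treatment | after TStart | after T4 | none stated |

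Neither reading reproduces the primary's windows.

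**3. Two children traced through the rules**

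- Child A: Grade 3 bleeding at minute 2, treated with another hemostat, Grade 0 at T4, T7 and T10, no later event.
- Child B: dry at minute 2, rebleeds at minute 3, study product reapplied as Protocol 6.1 allows, Grade 0 at T4, T7 and T10, no later event.

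| | Primary success | Treatment failure | T7/T10, list-wide | T7/T10, narrow | T7/T10, primary's two windows |
|---|---|---|---|---|---|
| A | No | Yes | **Yes** | No | No |
| B | Yes | No | Yes | **No** | Yes |

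The list-wide reading turns a rescued child into a T7 success although nothing changed between T4 and T7. The narrow reading turns a T4 success into a T7 failure, which a cumulative proportion should not allow. It also conflicts with Protocol 7.2.1.3.3, which dates hemostasis after a rebleed to the time the rebleeding stopped. The list-wide reading is therefore the more coherent of the two. Only the primary's two windows score both children consistently.

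**4. Size.** At 86 per arm, each child scored this way adds 1/86 = 1.16 points to that arm's rate. The documents give neither a T7 rate nor a pre-T4 rescue rate, so the counts below are assumptions. They take 76/86 (88.4%) in both arms as scored and move up to 3 rescued children to non-success: 3/86 = 3.5 points.

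Interval: exp{ln(RR) ± 1.96 × √(1/a − 1/86 + 1/b − 1/86)}, where a and b are the FS Grifols and EVICEL successes.

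| Scoring | FS Grifols | EVICEL | Ratio (95% CI) |
|---|---|---|---|
| As scored on the list-wide reading | 76/86 | 76/86 | 1.000 (0.897–1.115) |
| 3 rescued, all FS Grifols | 73/86 | 76/86 | 0.961 (0.854–1.080) |
| 3 rescued, all EVICEL | 76/86 | 73/86 | 1.041 (0.926–1.171) |
| 3 rescued in each arm | 73/86 | 73/86 | 1.000 (0.882–1.134) |

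The third row is the reciprocal of the second. With equal early rescue, both rates fall by 3.5 points and the ratio does not move.

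**The case against.** **The sentence does not force the error.** The closing window stands directly after reapplication and can be read as qualifying that item alone. Rescue and severe bleeding at any time would then disqualify, and child A could not be a T7 success. This stands: the text permits the mis-scoring but does not require it. It does not rescue the definition, because the same reading mis-scores child B.

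**The rest of the plan points to a TStart window for rescue.** The primary variable uses it, as did the primary endpoint of the three earlier pivotal trials (Protocol 2.2). The treatment-failure definition spans the whole 10 minutes. The scenario-table question on alternative treatment and Grade 3/4 bleeding has no split at T4. This makes the harmful programming less likely, but none of these places governs T7/T10.

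**The situation is narrow.** Only Grade 1 or 2 bleeding is enrolled, and alternative measures are barred in the 10 minutes except for Grade 3/4 breakthrough bleeding that endangers the child. Mis-scoring needs escalation and rescue within 4 minutes, then Grade 0 by T7 or T10 with no later event. The number may be zero.

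**The consequences are limited.** The decision rule based on 0.8 is written for the primary endpoint, and none is stated for T7/T10. Early rescues would still show among primary and treatment failures. This also stands.

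**Conclusion.** The T7/T10 definition is ambiguous, and neither reading matches the primary. On the more coherent reading, a child rescued before T4 can be scored a T7/T10 success of the assigned product. The effect is 1.2 points per child in that arm's rate, or 0 to 3.5 points under the assumed 0 to 3 children per arm at the planned 86.

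A reader might infer three stronger things that the documents do not support:

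- *That such children will be counted as successes.* The wording also allows the opposite scoring, and no rate of early rescue is given.
- *That the ratio is pulled toward 1, or toward FS Grifols.* The error raises the rate of whichever arm has more early rescues. It moves the ratio toward 1 only if that arm's rate would otherwise be the lower one, and it favours FS Grifols only if FS Grifols has the more early rescues.
- *That the non-inferiority conclusion is at risk.* The primary variable, its scenario table, the treatment-failure endpoint and the sample size already count rescue from TStart or do not depend on it.

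**What to change.** In SAP 3.1.2.1, Protocol 7.1.2.1 and the synopsis, give the T7/T10 definition the primary's two windows:

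- rebleeding or reapplication of study product disqualifies from T4 to TClosure;
- Grade 3/4 bleeding or alternative hemostatic treatment disqualifies from TStart to TClosure.

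Add T7 and T10 rows to the scenario table in SAP 3.1.1, including a child rescued before T4 and a child who rebleeds and has study product reapplied before T4.

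Reconcile the rebleeding clause with Protocol 7.2.1.3.3. State whether re-dating hemostasis to the end of a rebleed applies only to rebleeding before T4, since rebleeding after T4 is listed as disqualifying.

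The cost is one sentence in three places, a few table rows and one clarification, best settled before database lock. The primary endpoint already needs these events from TStart, so no new data and no change in sample size are needed. The downside is that T7 and T10 rates may be slightly lower. The change concerns scoring only, not treatment.
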